## 4.3 Treatment and Follow-up

In the first phase, patients will be randomized in equal proportions to receive six (6) instillations of either BCG or saline within a 10 week period of time. All patients will be followed for 34 weeks from randomization.

209210

211

212

- A variety of pharmacotherapeutic agents are utilized in the treatment of IC. This study will define as "IC Treatment Medications" those agents medically prescribed for treatment of IC symptoms in patients with an established diagnosis of interstitial cystitis.
- 213 These medications are identified in the following therapeutic categories:
- Tricyclic Antidepressants
- Sedating Antihistamines (H1 Blocker)
- Anticonvulsants
  - Alpha2-Adrenergic Agonist Agents
  - Intravesical therapies (e.g. DMSO, Clorpactin, Heparin)

218219

217

- 220 Prior to randomization, all patients will be stabilized on current medications.
- 221 Medications prescribed for treatment of IC from these therapeutic categories will be
- specifically identified in the patients pre-study diary record and monitored in the patients
- 223 concomitant medication record throughout the study. Additionally, if the patient is taking
- prescribed medications for treatment of IC that are not included in the above categories,
- these medications will also be identified and monitored as IC medications.
- 226
- Patients randomized into the study will be requested to have no change in their pre-study medication regimen for IC throughout the treatment and follow-up period. It is strongly recommended that categories of medications (as listed above), prescribed for the
- treatment of IC, be *avoided* in managing the patients IC symptoms throughout the trial.
- 231 Instead, *breakthrough* medications (as listed in 4.3.1) will be used to manage the patient's
- 232 IC symptoms throughout the trial. Other than the specified intravesical treatment
- administered in this study, the administration of any other intravesical treatment is
- prohibited during the course of this study.

235236

## 4.3.1 Definition and Classification of Breakthrough Medication

237238

239

240

241

- During the entire treatment and follow-up period (34 weeks), oral medications of the following therapeutic categories will be allowed, on a temporary as needed basis, for use as "breakthrough" medication for treating episodes of increase in pain, frequency, urgency/pressure (IC symptoms). For purposes of this clinical trial,
- "breakthrough" medication is defined as those agents utilized to symptomatically
   alleviate interstitial cystitis symptoms of pain, frequency, urgency/pressure as follows:

244245

246

247

- Narcotic Analgesics
- Urinary Analgesics
- Urinary Antispasmodics
- Analgesics, nonsteroidal anti-inflammatory drugs (NSAIDS)
- Analgesics, salicylate and miscellaneous
  - Anticholinergics
- Antibiotics (except: Aminoglycosides, Quinolones, Rifampin, Doxycycline, INH)

## 

# **4.4 Study Endpoints**254

## 4.4.1 Primary Endpoint

The primary endpoint on which the comparative efficacy of BCG and saline will be evaluated is a combined endpoint with two components: the patient-reported global assessment of response and the use of IC medications during the follow-up period.

The global evaluation of improvement for the primary endpoint will occur at week 34 or withdrawal, whichever comes first, relative to IC symptoms at baseline via the question: "As compared to when you started the study, how would you rate your interstitial cystitis symptoms now?" A seven point scale centered at zero will be used: -3) markedly worse; -2) moderately worse; -1) slightly worse; 0) no change; +1 slightly improved; +2) moderately improved; and +3) markedly improved. Participants who answer either +2) moderately improved or +3) markedly improved on the global evaluation will be considered to have evidence of "clinical improvement"

The second component relates to changes (increase or addition) in the use of IC treatment medications from the level at which the patient was stabilized at the beginning of the study. Increased usage of pre-study IC medications or the initiation of new IC medications during the last four weeks of post-treatment follow-up (week 31 - 34 post-randomization) will cause the patient to be classified as a non-responder.

Use of *breakthrough* medications as described in Section 4.3.1 will be allowed **with the exception of narcotic analgesics.** New or increased use of narcotic analgesics during the last four weeks of post-treatment follow-up (week 31-34) will be considered equivalent to starting a new IC medication, and therefore, would cause the patient to be classified as a non-responder. In addition, any patient who requests narcotic analgesics for treatment of IC symptoms during the last four weeks of post-treatment follow-up will also be classified as a non-responder.

Therefore, patients will be considered to be "responders" for the primary endpoint if they fulfill both of the following two criteria:

1. Report "moderate" or "marked" improvement on the global assessment at 34 weeks.

2. Report no increase in pre-study IC medications, and no initiation of new IC medications, and no new or increased use of narcotic medications during the final 4 weeks of the follow-up phase.

The proportion of responders in each treatment arm will be compared in an intent-to-treat analysis to evaluate the overall effectiveness of BCG. Criteria #1 and #2 must both hold for a patient to be considered a responder at 34 weeks; all other patients will be considered "non-responders" and included in denominators for evaluation of response rates between treatment arms. Specifically, participants who withdraw from the study for

any reason (e.g. adverse event or participant choice) prior to the primary endpoint, will be considered treatment non-responders for the primary endpoint.

299300301

298

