## 13 STATISTICAL CONSIDERATIONS

### **13.1 Study Design**

The proposed study design is a two-arm, double-blind, randomized clinical trial (RCT) to evaluate the effect of intravesical BCG, compared to intravesical saline placebo on IC symptoms. The primary analysis on which sample size requirements are based is the comparison of response rates for the composite primary outcome as defined in Section 4.4.1. For this comparison, we desire adequate numbers of participants to detect a difference in response rates between 30% and 50% (difference of 20%).

The primary endpoint for which the comparative efficacy of BCG and saline will be evaluated is a composite endpoint with two components: a) the patient-reported global assessment of response and b) the use of specified breakthrough medications for IC symptoms during the last four weeks of the follow-up period. The global evaluation of improvement for the primary endpoint will occur at week 34 or withdrawal, whichever comes first, relative to IC symptoms at baseline, via the question:

"As compared to when you started the study, how would you rate your Interstitial Cystitis (IC) symptoms now?"

A seven point scale, centered at zero, will be used, with categories as follows: -3) markedly worse; -2) moderately worse; -1) slightly worse; 0) no change; +1 slightly improved; +2) moderately improved; and +3) markedly improved. Participants who answer either +2) moderately improved or +3) markedly improved on the global evaluation are considered to have evidence of "clinical improvement", and will be classified as a "responder" for the global assessment portion of the primary endpoint.

The second component of the primary endpoint relates to changes (increase or addition) in the use of IC treatment medications from the level at which the patient was stabilized at the beginning of the study, and the use of "breakthrough" medications. Increased usage of pre-study IC medications, or the initiation of new IC medications, during the last four weeks of post-treatment follow-up (weeks 31 - 34 post-randomization), will cause the patient to be classified as a "non-responder." Use of *breakthrough* medications as described in Section 4.3.1 will be allowed during this time **with the exception of narcotic analgesics.** 

Therefore, patients will be considered to be "responders" overall for the primary endpoint if they fulfill both of the following two criteria:

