1. Report "moderate" or "marked" improvement on the patient-reported global assessment at 34 weeks.

2. Report no increase in pre-study IC medications, and no initiation of new IC medications, and no new or increased use of narcotic medications during the final 4 weeks (weeks 31-34) of the post-treatment follow-up phase.

The proportion of "responders" in each treatment arm will be compared in an intent-totreat analysis to evaluate the overall effectiveness of BCG. Criteria #1 and #2 must both hold for a patient to be considered a responder at 34 weeks; all other patients will be considered "non-responders", and will be included in denominators for evaluation of response rates between treatment arms. Specifically, participants who withdraw from the study for any reason (e.g. adverse event or participant choice) prior to the primary endpoint determination at 34 weeks, will be considered treatment "non-responders."

1219 1220

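### The medication criterion of the primary endpoint fails a patient for starting an IC drug in weeks 31-34, not for being on one, so a new non-narcotic IC drug started earlier and continued passes on a literal reading

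*Protocol*

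**What the plan says.** Protocol 4.4.1 introduces the second component as "the use of IC medications during the follow-up period". It then explains that the component concerns "changes (increase or addition) in the use of IC treatment medications from the level at which the patient was stabilized". The sentence that does the classifying is narrower: the disqualifying events are increased use of pre-study IC drugs or "the initiation of new IC medications during the last four weeks of post-treatment follow-up", identified as weeks 31-34. Numbered criterion 2 follows it: "no initiation of new IC medications, and no new or increased use of narcotic medications during the final 4 weeks of the follow-up phase". Section 13.1 repeats the baseline-level sentence, the classifying sentence and an essentially identical criterion 2, ending "no new or increased use of narcotic medications during the final 4 weeks (weeks 31-34) of the post-treatment follow-up phase".

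The label changes from place to place. Section 4.1 describes the component as breakthrough medication use and gives no window. Item (b) of 13.1 calls it "the use of specified breakthrough medications for IC symptoms during the last four weeks of the follow-up period". Yet both 4.4.1 and 13.1 go on to allow breakthrough drugs other than narcotics.

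The text of 4.4.1 adds that a patient who merely requests "narcotic analgesics for treatment of IC symptoms during the last four weeks of post-treatment follow-up will also be classified as a non-responder". Neither criterion 2 in 4.4.1 nor any part of 13.1 carries this.

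Section 4.3 states no responder rule, but it decides which drugs count. It lists the IC drug categories and says of other drugs prescribed for IC before the study that "these medications will also be identified and monitored as IC medications". It asks patients not to change their regimen and strongly recommends avoiding the listed categories. Only other intravesical treatment is prohibited there; 9.1 also bars pentosan polysulfate.

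**The concern.** The medication component is there so that improvement bought with added IC therapy is not credited to the randomized instillation. A test for an event in the window (initiation) does that only for drugs started in the last four weeks. A test for a state in the window (use above the baseline regimen) does it whatever the start date. The lead-in describes the second and the rule applies the first.

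Much hangs on the classification. It is the primary outcome, it feeds the interim efficacy look (13.5.1), and under 10.5 it decides who is offered open-label BCG in Phase 2 and who is not. Section 10.4.3 has the site's principal investigator and coordinator determine response, and there are nine sites (13.3), so an ambiguous rule can be resolved in different ways.

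**Working it through.** **Step 1: score the same patient under each statement.** Every patient below rates +2 or +3 at week 34.

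| Patient | Lead-in or text | Classifying rule, criterion 2 |
|---|---|---|
| A. New tricyclic at week 20, still taken at week 34 | Addition to the baseline level: non-responder | Nothing initiated in weeks 31-34: responder |
| B. Pre-study IC drug raised at week 20, still raised at week 34 | Increase from baseline: non-responder | Increased use in the window: can be read as non-responder |
| C. Requests narcotics in week 32, takes none | 4.4.1 text: non-responder | No new or increased use: responder |
| D. Starts a non-narcotic breakthrough drug in week 32 | 4.1 and 13.1(b) labels suggest it counts | Allowed by 4.4.1 and later in 13.1 |
| E. Anticholinergic prescribed for IC before the study, raised in week 32 | IC medication under 4.3: non-responder | Same class started new as needed under 4.3.1: allowed |

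Patient A shows the substantive gap. It is confined to newly started, non-narcotic IC drugs, and it runs from randomization to week 30, so the treatment weeks are as uncovered as the follow-up weeks. Patients C and D are conflicts between passages. Patient E is an overlap between two drug lists.

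**Step 2: reproduce the design.** Inputs from 13.1 and 13.2: 30% v 50%, two-sided 0.05, 80% power, increases of 20% for clustering and 5% for interim monitoring.

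- Uncorrected: n = [1.960 × √(2 × 0.4 × 0.6) + 0.842 × √(0.3 × 0.7 + 0.5 × 0.5)]² / 0.20² = 93.0 per arm.
- Continuity-corrected: (93.0 / 4) × [1 + √(1 + 4 / (93.0 × 0.20))]² = 102.8, so 103. This matches the table.
- Inflated: 103 × 1.20 × 1.05 = 129.8, so 130 per arm and 260 in total. This matches.
- Exact power of the two-sided Fisher test at 103 per arm, by full enumeration: 81.1%.

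The illustration uses 103 per arm because the step from 103 to 130 is already allotted to clustering and interim monitoring.

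**Step 3: illustrate what misclassification could do.** The protocol gives no rate of earlier additions, so every share here is an assumption.

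| Assumption | Saline v BCG | Fisher power, 103 per arm |
|---|---|---|
| None | 30% v 50% | 81% |
| Saline only, +3 points | 33% v 50% | 66% |
| Saline only, +5 points | 35% v 50% | 55% |
| Saline only, +10 points | 40% v 50% | 26% |
| 5% of non-responders in both arms | 33.5% v 52.5% | 76% |
| 10% of non-responders in both arms | 37% v 55% | 69% |
| 15% of non-responders in both arms | 40.5% v 57.5% | 63% |

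The both-arms rows add f × (1 − p) to each rate p. At f = 10%, for example, 0.30 + 0.10 × 0.70 = 0.37 and 0.50 + 0.10 × 0.50 = 0.55.

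**The case against.** The best defence is that the text, read as a whole, already means change from baseline. Both 4.4.1 and 13.1 name the stabilized level as the reference and speak of addition as well as increase. Section 13.1 says the outcome is the one defined in 4.4.1, so 4.4.1 governs, the label in 13.1(b) is a slip, and leaving the request rule out of a summary list does not repeal it. Much of this stands. A reader might infer that the criterion catches nothing that began before week 31. The documents do not support that: raised use of a pre-study drug that persists into the window can be read as caught, and so can new or increased narcotic use. A reader might also take 4.3 for a further, conflicting statement of the endpoint. It states none; the differing labels are in 4.1 and 13.1(b).

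The defence does not rescue patient A. No sentence says that a new drug started before week 31 and continued is a failure. One could try to attach the four-week limit in criterion 2 to the narcotics clause alone, but the classifying sentence in 4.4.1 ties initiation to the window expressly.

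Two further objections reduce the scope. Treating a stabilized regimen differently from temporary as-needed drugs is partly deliberate, and inclusion criterion 3 lists potential previous therapies, not current ones, so patient E needs clarification but is not proof of a contradiction. The power figures also rest on assumed shares. The 30% placebo rate may already include some added medication. Nor need additions be confined to saline: the appended package insert reports bladder irritability in about 60% of TICE BCG recipients, in a bladder cancer setting, so BCG patients may add drugs too.

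**Conclusion.** The point holds as a defect of wording in the primary endpoint. As written, a new non-narcotic IC drug started between randomization and week 30 and still taken in weeks 31-34 does not disqualify a patient, contrary to the stated purpose of the component. Around this sit two inconsistencies: the breakthrough label in 4.1 and 13.1(b), and the narcotic-request rule that appears only in the text of 4.4.1.

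Its size cannot be derived. A reader might infer that the gap must inflate the saline rate and cost the trial power. That is plausible, because 4.3 discourages but does not forbid most additions, but the protocol gives neither a rate nor a direction. The fall from 81% to between 66% and 26% rests on an assumed 3 to 10 points in the saline arm with BCG fixed at 50%. With equal shares of non-responders reclassified in both arms, the loss is smaller, to between 76% and 63%. What needs no assumption is that the rule affects who counts as a responder and that the passages can be read in more than one way.

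**What to change.** State criterion 2 once, as a condition in the window relative to baseline, for example:

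*During weeks 31-34: no use of any IC treatment medication that was not in the regimen recorded at randomization, and none above its recorded level, whenever the change began; no narcotic use above the recorded level; and no request for narcotics for IC symptoms.*

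- Put this text verbatim into the numbered criteria of both 4.4.1 and 13.1.
- In 4.1 and 13.1(b), replace the breakthrough label with IC treatment medications and narcotics.
- Reconcile 4.3 and 4.3.1 on how to score a class that is both a baseline IC medication and an allowed breakthrough class.

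Making any use of a prohibited therapy since randomization a failure would be a new endpoint rule, not a reconciliation, and is not proposed here.

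The cost is a wording change and a revised response derivation; the sample size does not change. Concomitant medication is already monitored throughout the study. Observed response rates may be slightly lower in both arms. The sponsor should confirm that requests for narcotics are captured on a form, since the visit schedule in Appendix B does not identify one that records them.

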## 4.4.2 Secondary Endpoints

302 303

304

305

306

307

308

309

Secondary endpoints will include symptom indices, quality of life, and biomarkers. All of these will be assessed repeatedly during the treatment and follow-up period. The schedule of follow-up data collection is shown in the study procedures table. Analyses will include changes over time using longitudinal data models, and associations between these changes and overall patient response as defined above. The latter analyses will involve a component of validation of the symptom indices. Furthermore, changes in biomarkers will be correlated with changes in symptoms to evaluate possible mechanisms of effects. Details of these analyses are given in the Statistical Considerations section.

310311

## **6 PARTICIPANT CRITERIA**

331332

## **6.1 Participant Recruitment**

333334

335

336

337

338

339

340

Participant recruitment will be conducted through the urology clinic at each of the designated clinical sites. Participants may be self-referred or referred through their primary physician (either solicited or unsolicited by the urology clinic). Participants referred to the clinics with refractory symptoms of IC will be introduced to the ICCTG protocol and asked whether they are interested in participating in the study. Interested subjects will be asked to sign the informed consent form (See Appendix A Suggested Subject Consent Form), approved by the local Institutional Review Board (IRB). This form will provide consent for both the screening and the follow-up procedures.

## **6.2 Study Population and Number of Participants**

The study population for this RCT #2 protocol will be drawn from participants with a diagnosis of IC, confirmed sometime in the past with the results from a cystoscopy/hydrodistention. It is expected that 260 participants will be accrued within a 14 month time period from the start of the study. (See Section 13.2).

Any IC participant presenting with symptoms of urinary frequency in conjunction with urinary pain/discomfort persisting for at least 24 weeks will be considered a candidate for enrollment into the study. Participants must satisfy the following eligibility criteria in order to be entered into this study.

### 6.2.1 Inclusion Criteria

- 1. At least 18 years of age.
- 2. Participant must sign and date the informed consent.
- 3. Participant must have received a minimum of 12 weeks of treatment with some standard form of therapy or combination of therapies for IC. The treatment must have occurred after diagnosis of IC and administered in response to the patient's IC symptoms. Potential previous therapies include: tricyclic antidepressants, hydroxyzine, other antihistamines, DMSO, pentosanpolysulfate, heparin, NSAIDS, and anticholinergies.
- 4. Participant (male or female) must agree to use a medically approved method of birth control.
- 5. Participant must report a urinary frequency of at least 11 times per 24-hour day, on average over the previous four weeks. This frequency criterion must be met at each of the two baseline-screening visits as reported by the participant.
- 6. Participant must report a pain/discomfort score of 4 or greater on a 0 9 Likert scale. This pain/discomfort criterion must be met at each of the two baseline-screening visits.
- 7. These reported urinary symptoms of frequency and pain/discomfort must have been present for at least the previous 24 weeks prior to the first baseline screening visit.
- 8. Participants must report in the baseline voiding diary at least one voided volume greater than or equal to 75cc in a 24 hour period.

### 6.2.2 Exclusion Criteria

Any participant satisfying one of the following criteria will **not** be eligible to participate in the ICCTG Study:

- 1. Active tuberculosis that requires ongoing therapy
- 2. Immunocompromised patients and/or known positive HIV test results.
- 3. Known allergy to or intolerance of BCG, or any of its components as reported by the participant or derived from their medical records.
- 4. Previously treated with intravesical BCG.

389 5. Unable to void spontaneously.

- 6. Any imminent change in residence, which could compromise compliance.
- 7. Unlikely to be compliant due to unmanaged medical or psychological problem including dementia, aphasia or other deficits of cognition or speech/language function that will interfere with her/his ability to complete study.
- 8. Substance abuse or dependency problem within the past 2 years for which patient received no treatment.
- 9. Severe debilitating concurrent medical conditions including severe coronary artery disease, azotemia, moderate to severe hepatic insufficiency, systemic cancer requiring treatment, or similar severe conditions.
- 10. Previous treatment with Cytoxan®/cyclophosphamide.
- 11. A history of pelvic radiation treatment, bladder calculus, tuberculous cystitis, neurologic disease affecting bladder function, bladder cancer or cancer in situ, or urethral cancer. Any other neoplastic process currently requiring systemic, non-prophylactic treatment.
- 12. Previous augmentation cystoplasty, cystectomy or cystolysis, neurectomy (i.e. hypogastric nerve plexus ablation) or implanted peripheral nerve stimulator which has affected bladder function.
- 13. Currently has an active urethral calculus, ureteral calculus, urethral diverticulum.
- 14. A current history of visicoureteral reflux.

